# 8.5 AE/SAE Reporting Period and Parameter

Safety events are reported from the time of study injection (Day 0) through completion of the study at Day 90. Specifically, solicited AEs to assess local and systemic reactogenicities will be collected at 30 minutes and then daily for 3 days thereafter. If a solicited AE started during the 3 days post-vaccination and continues beyond the 3 days it will continue to be reported as a solicited AE. Unsolicited AEs and SAEs will be reported from Day 0 through the end of the study at Day 90.

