## 8.11 Clinical evaluations

#### 8.11.1 Vital Signs

The vital signs in this study include temperature in degrees Celsius (recorded to the nearest 0.1 degree) by oral thermometer; blood pressure in millimetres of mercury; and heart rates in beats per minute, measured by automated device or manually.

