#### **Stopping rules:**

The occurrence of one or more of the following criteria will automatically pause or halt further vaccinations in the study:

- 1. One or more subjects experience a serious adverse event (SAE) that is suspected to be vaccine related.
- 2. One or more subjects experience a grade 4 injection site reaction (such as necrosis or sterile abscess at injection site requiring surgical intervention) that is suspected to be vaccine related.
- 3. Ten or more subjects experience a grade 3 or greater reactogenicity event following vaccination that is suspected to be vaccine related.
- 4. Five or more subjects experience the same grade 3 or more clinical abnormality following vaccination that is expected to be vaccine related

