- Grade 2	xx(xx.xx)	xx(xx.xx)
- Grade 3	xx(xx.xx)	xx(xx.xx)
- Grade 4	xx(xx.xx)	xx(xx.xx)
p - value = x.xxxx		
Day 7		
- Grade 0		
- Grade 1		
- Grade 2		
- Grade 3		
- Grade 4		
p - value =		
Day 21		
- Grade 0		
- Grade 1		
- Grade 2		
- Grade 3		
- Grade 4		
p - value =		
Day 90		
- Grade 0		
- Grade 1		
- Grade 2		
- Grade 3		
- Grade 4		
p - value =		

TREF 3.1: Comparison of Temperature Grading at Follow up Visit by GPO Tri Fluvac and Active Comparator Group

Note: Grading of reporting temperature are:

Grade 0: (no) < 38 °C Grade 1: (mild) 38.0 °C - < 38.6 °C Grade 2: (moderately high) \ge 38.6 °C - < 39.3 °C Grade 3: (high) \ge 39.3 °C - < 40.0 °C Grade 4: (Potential Life Threatening) > 40 °C

	Tri fluvac	Comparator	
Follow up Visit	(N = xx)	(N = xx) n (%)	
-	n (%)		
30 min.			
- Grade 0	xx(xx.xx)	xx(xx.xx)	
- Grade 1	xx(xx.xx)	xx(xx.xx)	
- Grade 2	xx(xx.xx)	xx(xx.xx)	
- Grade 3	xx(xx.xx)	xx(xx.xx)	
- Grade 4	xx(xx.xx)	xx(xx.xx)	
p - value = x.xxxx			
Day 1			
- Grade 0			
- Grade 1			
- Grade 2			
- Grade 3			
- Grade 4			
p - value =			
Day 2			
- Grade 0			
- Grade 1			
- Grade 2			
- Grade 3			
- Grade 4			
p - value =			
Day 3			
- Grade 0			
- Grade 1			
- Grade 2			
- Grade 3			
- Grade 4			
p - value =			

TREF 3.2: Comparison of Temperature Grading at Post Immunization by GPO Tri Fluvac and Active Comparator Group

Note: Grading of reporting temperature are:

Grade 0: (no) < 38 °C Grade 1: (mild) 38.0 °C - < 38.6 °C Grade 2: (moderately high) \ge 38.6 °C - < 39.3 °C Grade 3: (high) \ge 39.3 °C - < 40.0 °C Grade 4: (Potential Life Threatening) > 40 °C

Vital Sign	Da	ay 0	Da	ay 7	Da	y 21	Da	y 90
	Tri fluvac (N = xx)	Comparator (N = xx)	Tri fluvac (N = xx)	Comparator (N = xx)	Tri fluvac (N = xx)	Comparator (N = xx)	Tri fluvac (N = xx)	Comparator (N = xx)
Temperature (°C)								
n	XX	XX						
Mean(SD)	xx.xx(xx.xx)	xx.xx(xx.xx)						
Median	XX.XX	XX.XX						
Min, Max	XX.XX , XX.XX	XX.XX , XX.XX						
P- value =	X.X	xxxx						
Pulse (Beats per								
n								
Mean(SD)								
Median								
Min, Max								
P- value =								
Blood Pressure								
Systolic (mmHg)								
n								
Mean(SD)								
Median								
Min, Max								
P- value =								
Diastolic								
n								
Mean(SD)								
Median								

TREF 3.3: Vital Sign at Follow up Visit by GPO Tri Fluvac and Active Comparator Group

TREF 3.3: Vital Sign at Follow up Visit by GPO Tri Fluvac and Active Comparator Group (Continue)

Vital Sign	D	ay 0	D	ay 7	Da	ay 21	Da	ıy 90

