	Tri fluvac (N = xx)	Comparator (N = xx)	Tri fluvac (N = xx)	Comparator (N = xx)	Tri fluvac (N = xx)	Comparator (N = xx)	Tri fluvac (N = xx)	Comparator (N = xx)
Min, Max								
P- value =								

	D	Day 0 Day 7		Day 21		Day 90		
	Tri fluvac (N = xx)	Comparator (N = xx)	Tri fluvac (N = xx)	Comparator (N = xx)	Tri fluvac (N = xx)	Comparator (N = xx)	Tri fluvac (N = xx)	Comparator (N = xx)
HEENT, n (%)								
Normal	xx(xx.xx)	xx(xx.xx)						
Abnormal	xx(xx.xx)	xx(xx.xx)						
P- value =	X.2	xxxx						
Lungs, n (%)								
Normal								
Abnormal								
P- value =								
Cardiovascular, n (%)								
Normal								
Abnormal								
P- value =								
Gastrointestinal, n (%)								
Normal								
Abnormal								
P- value =								
Musculoskeletal, n (%)								
Normal								
Abnormal								
P- value =								
Skin, n (%)								
Normal								
Abnormal								
P- value =								

TREF 3.4: Physical Examination by GPO Tri Fluvac and Active Comparator Group

	Day 0		D	Day 7		Day 21		Day 90	
	Tri Fluvac (N = xx)	Comparator (N = xx)	Tri Fluvac (N = xx)	Comparator (N = xx)	Tri Fluvac (N = xx)	Comparator (N = xx)	Tri Fluvac (N = xx)	Comparator (N = xx)	
Neurologic, n (%)	X	((
Normal	xx(xx.xx)	xx(xx.xx)							
Abnormal	xx(xx.xx)	xx(xx.xx)							
P- value =	X XXXX								

TREF 3.4: Physical Examination by GPO Tri Fluvac and Active Comparator Group (Continue)

TREF 3.5: Comparison of Maximum Grade of Any Local Reaction at Post Immunization by GPC
Tri fluvac and Active Comparator Group

Grade		Tri Fluvac (N = xx) n (%)	Comparator (N = xx) n (96)
Grada 0			
Grade 0		XX(XX.XX)	XX(XX.XX)
Grade 1		XX(XX.XX)	XX(XX.XX)
Grade 2		xx(xx.xx)	xx(xx.xx)
Grade 3		xx(xx.xx)	xx(xx.xx)
P- value =	X.XXXX		

Note: - Any local reaction on any day (by case)

- Erythema and Induration will be not included.

- Grading

- Grade 0 none
- Grade 1 mild
- Grade 2 moderate
- Grade 3 severe

TREF 3.6: Comparison of Local Reaction at Post Immunization each Follow up Time by GPO Tri Fluvac and Active Comparator Group

	30	min	D	Day 1	D	ay 2	Da	ny 3
Local Reaction	Tri Fluvac	Comparator						
	(N=xx)							
- Pain, n (%)	xx(xx.x)	xx(xx.xx)						
p-value =	X.:	xxxx						
- Limitation of arm movement, n (%)								
p-value =								
- Erythema (cm.)								
n								
Mean(SD)								
Median								
Min, Max								
p-value =								
- Swelling (cm.)								
n								
Mean(SD)								
Median								
Min, Max								
p-value =								
- Induration (cm.)								
n								
Mean(SD)								

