Median								
Min, Max								
p-value =								

Note: - Summary by case who had symptoms

TREF 3.7: Comparison of Maximum Grade of Local Reaction by Symptom at Post Immunization
by GPO Tri fluvac and Active Comparator Group

Lo	ocal Reaction		Tri fluvac (N=xx)	Comparator (N=xx)
Pain,	n (%)			
Grad	de 0		xx(xx.xx)	xx(xx.xx)
Grad	de 1		XX(XX.XX)	xx(xx.xx)
Grad	de 2		xx(xx.xx)	xx(xx.xx)
Grad	de 3		XX(XX.XX)	xx(xx.xx)
	p-value =	X.XXXX		
Limi	tation of arm movemen	ıt, n (%)		
Grad	de 0			
Grad	de 1			
Grad	de 2			
Grad	de 3			
	p-value =			
Note:	- On any day (by cas	es)		
	- Grading	,		
	Grada 0 por	no		
	Grade 1 mi	le Id		
	Grade 2 mg	nderate		
	Grade 3 - set	nere		
	Grade 5 - sev			

Number of Days by Local Reaction	Tri fluvac (N = xx)	Comparator (N = xx)	
Pain			
only 30 min.	xx (xx.xx)	xx (xx.xx)	
1 day	xx (xx.xx)	xx (xx.xx)	
2 days	xx (xx.xx)	xx (xx.xx)	
3 days	xx (xx.xx)	xx (xx.xx)	
p-value = x.xxxx			
Limitation of arm movement			
only 30 min.	xx (xx.xx)	xx (xx.xx)	
1 day	xx (xx.xx)	xx (xx.xx)	
2 days	xx (xx.xx)	xx (xx.xx)	
3 days	xx (xx.xx)	xx (xx.xx)	
p-value = x.xxxx			

TREF 3.8: Comparison Number of Subject by Number of Local Reaction Days at Post Immunization GPO Tri fluvac and Active Comparator Group

Note: - Subjects who had symptom with local reaction will be considered in this table.

- Number of subjects who had symptom will be compared between Tri fluvac and comparator.

- Percentage will be calculated from total enrollment subject.

TREF 3.9: Comparison Number of Subjects by Number of Local Reaction at Post Immunization
GPO Tri fluvac and Active Comparator Group

Number of Local Reaction	Tri fluvac (N = xx)	$\begin{array}{l} \textbf{Comparator} \\ \textbf{(N = xx)} \end{array}$
No symptom	xx (xx.xx)	xx (xx.xx)
1 symptom	xx (xx.xx)	xx (xx.xx)
2 symptoms	xx (xx.xx)	xx (xx.xx)
p-value = x.xxxx		

Note: - All enrollment Subjects will be considered in this table. - Percentage will be calculated from total enrollment subject.

TREF 3.10: Comparison of Maximum Grade of Any Systemic Reaction at Post Immunization by GPO Tri fluvac and Active Comparator Group

Create	Tri fluvac	Comparator	
Grade	(N=xx)	(N=xx)	
	n (%)	n (%)	
Grade 0	xx(xx.xx)	xx(xx.xx)	
Grade 1	xx(xx.xx)	xx(xx.xx)	
Grade 2	xx(xx.xx)	xx(xx.xx)	
Grade 3	xx(xx.xx)	xx(xx.xx)	
P-value = x.xxxx			

Note: Grading

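### The SAP reaction tables do not match the protocol's grading: 40.0 °C has no fever grade, local grades stop at 3, the systemic scale rests on conflicting protocol text, and duration rows differ

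*SAP*

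**What the plan says.** **Fever.** The notes to SAP TREF 3.1 and 3.2 end grade 3 below 40.0 °C and give the last grade as "Grade 4: (Potential Life Threatening) > 40 °C". Protocol 8.6 refers temperature grading to Appendix A, where non-axillary grade 4 starts at 40.0 °C inclusive. Section 8.11.1 specifies "temperature in degrees Celsius (recorded to the nearest 0.1 degree) by oral thermometer".

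**Local reactions.** Protocol 8.2 grades solicited local and systemic events by Appendix A. That table defines grade 4 for injection-site pain, for erythema and, by reference, for induration/swelling. In the SAP, the note to TREF 3.5 ends at "Grade 3 severe" and leaves out erythema and induration. TREF 3.7 grades only pain and limitation of arm movement, also 0–3. TREF 3.6 reports erythema, swelling and induration in centimetres. Stopping rule 2 in protocol 9.3 is triggered when "One or more subjects experience a grade 4 injection site reaction" that is suspected to be vaccine related.

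**Systemic reactions.** TREF 3.10 and 3.12 use grades 0–3. Protocol 8.6 gives a four-level 0–3 scale for these symptoms. Appendix A, reached through 8.2, defines grade 4 for fatigue/malaise, nausea, vomiting and headache, and marks it not applicable for chills.

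**Duration.** TREF 3.8 (local) has rows for 30 minutes only and for 1, 2 and 3 days. TREF 3.13 (systemic) runs to 5 days. Under protocol 8.5, a solicited event that starts in the window and "continues beyond the 3 days it will continue to be reported as a solicited AE".

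**The concern.** Solicited local and systemic reactions are primary safety endpoints. They are to be summarised by severity, and the percentages with solicited events are to be compared between arms with p-values. A maximum-grade table should have a row for every grade that its scale can produce, and a grading rule should assign each recordable value to exactly one grade. Where the shells fail this, the programmer has to choose a category once data exist, and two programmers could choose differently. The mismatch sits at the severe end of the scale, where a single event matters most: one grade 4 injection-site reaction can halt vaccination, and 9.2 sends grade 4 erythema or induration for expedited review.

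**Working it through.** No sample size or power figure depends on this point. The check compares categories.

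**1. Fever boundary.** Take every 0.1 °C value from 35.0 to 42.4 °C, which is (42.4 − 35.0)/0.1 + 1 = 75 values, and count how many fall in each grade.

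| Grade | SAP range | SAP count | Appendix A count |
|---|---|---|---|
| 0 | below 38.0 | 30 | 30 |
| 1 | 38.0 to 38.5 | 6 | 6 |
| 2 | 38.6 to 39.2 | 7 | 7 |
| 3 | 39.3 to 39.9 | 7 | 7 |
| 4 | SAP from 40.1; Appendix A from 40.0 | 24 | 25 |
| Total | | 74 | 75 |

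The SAP leaves 75 − 74 = 1 value ungraded, namely 40.0 °C. It is also the only value on which the two rules differ. The 0.1 °C resolution is stated for vital signs. The diary thermometer's resolution is not stated, but 40.0 °C is a possible reading at any usual resolution.

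**2. Local grades.** Grade 4 rows: none in TREF 3.5 and none in TREF 3.7. By contrast, TREF 3.1 and 3.2 do have a grade 4 row for temperature. Adding a row for pain alone would not cover the case that rule 2 describes. One of its examples is necrosis, which Appendix A grades under erythema, and that is a reaction that TREF 3.5 excludes and TREF 3.7 does not list. The size limits in Appendix A (2.5, 5 and 10 cm) separate grades 1 to 3. Grade 4 there depends on clinical consequence, so it has to come from the event record. TREF 3.5 does not say whether swelling counts.

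**3. Systemic grades.** Grade 4 rows: none in TREF 3.10 and none in TREF 3.12. This agrees with the scale in protocol 8.6 and disagrees with 8.2 and Appendix A. The SAP cannot match both.

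**4. Duration.** The SAP's post-immunization columns are 30 minutes and Days 1, 2 and 3 (TREF 3.6 and 3.11), so the diary alone yields at most 3 days. If duration is counted from the diary, the 4- and 5-day rows of TREF 3.13 cannot be filled. If continuing reactions are counted past Day 3, TREF 3.8 lacks rows and TREF 3.13 has none above 5 days. Under either reading, one of the two tables is wrong.

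**The case against.** The strongest reply is that little would be lost. TREF 2.2 has a life-threatening row, and Appendices 04 and 05 list each local and systemic reaction with its day and grade, with no stated cap. A reader might infer from TREF 3.5 and 3.7 that a grade 4 reaction would be missing from the final report. The documents do not support that. The listings could show it, and so could TREF 2.2 if solicited reactions count as adverse events there, which the SAP does not say. This part of the reply stands, and it confines the gap to the reaction-grade tables.

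A reader might also infer that the SAP wrongly dropped grade 4 for systemic symptoms. It follows 8.6; the conflict is inside the protocol. That reply stands too.

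On duration, 8.5 is a rule of classification and not of counting, the diary covers Days 0–3, and duration is not a listed safety endpoint. This is fair, and it means that the duration rows do not understate the severity endpoint. It does not explain why two tables built on the same diary end at different days.

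Finally, the phase I/II results in protocol 2.4 report no fever in either arm over 90 days and describe the pain (32.5% of vaccine recipients) as mild. Readings of 40.0 °C and grade 4 pain should be very rare.

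**Conclusion.** The point holds as a consistency fault in the safety shells. Two parts contradict the governing table: the fever boundary, by exactly one recordable value, and the local tables, which lack grade 4 and do not grade erythema or induration. The systemic part is a contradiction between protocol 8.6 and protocol 8.2 with Appendix A, which must be reconciled before either scale can be called correct. The duration part is a mismatch between TREF 3.8 and TREF 3.13.

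The effect is limited to safety reporting. Expected counts are small, on the assumption that reactions resemble those in phase I/II. The documents give no rate for reactions that last beyond Day 3, so no number of affected participants can be stated. A reader might infer that safety is materially understated or that the main conclusion is at risk. Neither follows: the severe events have other places to appear, and the non-inferiority analysis uses none of these tables.

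**What to change.** 1. In the TREF 3.1 and 3.2 notes, change the grade 4 boundary to 40.0 °C or above, as in Appendix A. All 75 values in the check then receive one grade.
2. Add a grade 4 row to TREF 3.5 and 3.7. Tabulate Appendix A grades for erythema and induration/swelling, using the sizes already recorded and taking grade 4 from the clinical record. State how limitation of arm movement is graded, since the public copy of Appendix A shows no separate row for it.
3. Reconcile the systemic scale in protocol 8.6 with 8.2 and Appendix A, then make TREF 3.10 and 3.12 match the agreed scale.
4. Give TREF 3.8 and 3.13 the same rows with an open top category, for example 'continuing after Day 3'. The Day 7 diary review is the natural source. Confirm that the CRF records continuation for each solicited symptom, because Appendices 04 and 05 show no stop-date column.
5. State whether solicited reactions are counted in TREF 2.2.

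The cost is one inequality sign, a few table rows and one protocol clarification. No visit, sample or sample-size change is needed. The only possible data addition is a continuation field, if the CRF lacks one.

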## Table 2: Study Schedule and activities

Procedures	Study Day						
		D0	D7	D21	D60	D90	
			(-3, +7)	(+7)	(+14)	(+7)	
	Screening e	Immunization e					
Informed consent	X						
Assessment of entry criteria	Х	(X) f					
Medical history, AE/SAE, Concomitant medication	Х	(X) f	X	Х	Х	Х	
Vital signs	Х	(X) f	Х	Х		Х	
Urine pregnancy test a	Х	(X) f					
Physical examination a	Х	(X)	(X)	(X)		(X)	
Immunization		X					
Diary card b		X (Day 0-3)	X				
Blood for Immune response (HI Assay) (3ml)		X		Х		Х	
Phone call visit c					Х		
Influenza subtype by RT- PCR d			(X)	(X)	(X)	(X)	

Remark

a. Only at screening, the rest when the history suggested [(x) = Optional as indicated by medical history].

b. Diary card will be provided to the subjects for recording reactogenicity for 3 days after vaccination (Day 0-3) and return to review at Day 7.

c. At Day 60, adverse events and influenza-like illness (ILI) will be followed-up by phone call.

d. Determination of influenza subtype by RT-PCR will be done when the ILI is confirmed [(x) = Optional as indicated].

e. Screening day can be the same day as immunization day (D0)

f. Will be done if immunization is not performed on screening day

(x) Optional

ETHICS COMMITTEE FACULTY OF TROPICAL MEDICINE MAHIDOL UNIVERSITY

APPROVED

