# 7.4 Follow-up visits

# 7.4.1 Day 7(-3, +7 days) after Injection: Return the diary card

Subjects will return to the clinic on day 7 to return the diary card and report any adverse events. Subjects will be asked to report any adverse events that occur during the first seven days after immunization. Concomitant medication information will be collected.

At this visit;

- 1. Study staff will confirm participant identity.
- 2. Study staff will review the participant diary card and interim history with the participant and inquire about any new medical events since medical histories were last updated. Any AEs that have occurred and meeting reporting intensity will be recorded in the appropriate section(s) of the CRF. Diary card information will be entered into the CRF.
- 3. The participant will have temperature, pulse rate, and blood pressure recorded. A study clinician will perform a targeted (symptom based) physical examination and record the information on the CRF. Results will be reviewed by study staff and with the participant.
- 4. The participant will be instructed to inform the investigator as soon as possible if he/she experiences an AE requiring medical care and to seek medical care as appropriate. If the participant visits a health care provider, the participant should be sure to inform the health care provider of participation in this study and give the health care provider the contact information for the investigator.
- 5. There are no scheduled visits at week 2 after vaccination. Participants may be asked to come to the study clinic if the investigator follows up on any clinical issue. The participant will inform the study clinic of any medical events and seek medical care as needed. The participant will be instructed to give any health care provide they see the contact information for the investigator. FACULTY OF TROPICAL MEDICINE วิตยาลัยม

MAHIDOL UNIVERSITY

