# 8.11.3 Physical Examination

# General Physical Examinations

Qualified study clinicians will conduct a physical examination of all participants at S1. This physical examination will include the following:

- Recording of general appearance
- Physical examination of all organ systems. This includes the following:
  - Brief neurologic examination
  - Chest auscultation
  - Examination of lymph nodes (axillary and cervical)
  - Heart auscultation
  - Abdomen palpation (to check for liver size)
  - Measurement of the following vital signs:
    - body temperature
    - blood pressure
    - pulse/heart rate

\* Elevated blood pressure not greater than Grade 1 (Systolic  $\geq$ 140-159 or diastolic >90-99) will not be considered to be exclusionary at screening unless judged to be clinically significant by the PI or clinician designee.

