# Targeted Physical Examination

The Targeted Physical examination (PE) focuses on symptoms reported by the participant and the presence or absence of local and systemic reactogenicity. If no symptoms are reported by the participant, the Targeted PE does not need to be performed.

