# **10.5 Prevention and treatment**

All enrolled participants must be verified healthy by medical history evaluation, physical examination. Additionally, in order not to enroll pregnant woman, urine pregnancy test must be performed at the screening visit and prior to study vaccination.

At the follow up visit, the assessment of vital signs, physical examination (if indicated by history) and clinical follow up will be performed and all reported adverse events would be assessed. The study investigators will be experienced in monitoring and managing the safety of participants.

The investigator or other physician in attendance will administer therapy as clinically indicated. All adverse events will be followed until resolved, or until a stable situation has been reached. Adverse events that occurred during the study and which had not resolved at the last study visit will be followed until they have abated, or until a stable situation has been reached.

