n Mean(SD)							
Median							
Min May							
Iviiii, Iviax	D value -						
PMI	r - value –						
DMI							
n Mean(SD)							
Median							
Min May							
Ivini, Iviax	D- value =						
Tomporatura							
i emperature	(0)						
n M (CD)							
Mean(SD)							
Median							
Min, Max	D 1						
	P-value =						
Pulse (Beats p	er minute)						
n							
Mean(SD)							
Median							
Min, Max							
	P- value =						
Blood Pressur	re						
Systolic (mmI	Hg)						
n							
Mean(SD)							
Median							
Min, Max							
	P- value =						

TREF 1.3: Vital Sign at Screening by GPO Tri fluvac and Active Comparator Group

		All subjects	Screen Failed	Tri fluvac	Comparator
		(N = xx)	(N = xx)	(N = xx)	(N = xx)
Diastolic					
n					
Mean(SD)					
Median					
Min, Max					
	P- value =				

TREF 1.3: Vi	ital Sign at Screen	ing by GPO	Tri fluvac and Active	Comparator Group (Co	ontinue)
	8				,

Note: Enrolled cases will be compared between GPO Tri fluvac and Active Comparator.

				E nr	olled
		All subjects (N=xx)	Screen Failed (N=xx)	Tri fluvac (N = xx)	Comparator (N = xx)
HEENT. n ((%)				
Normal	,	xx(xx.xx)	xx(xx.xx)	xx(xx.xx)	xx(xx.xx)
Abnormal		xx(xx.xx)	xx(xx.xx)	xx(xx.xx)	xx(xx.xx)
	P- value = $x.xxxx$				
Lungs, n (%	ó)				
Normal					
Abnormal					
	P- value =				
Cardiovasc	ular, n (%)				
Normal					
Abnormal					
	P- value =				
Gastrointes Normal Abnormal	tinal, n (%)				
	P- value =				
Musculoske Normal Abnormal	letal, n (%)				
	r - value -				
Skin, n (%) Normal Abnormal	P- value =				
Neurologic	n (%)				
Normal Abnormal	ш (70)				
	P- value =				
Other Normal Abnormal p-value =					

TREF 1.4: Physical Examination at Screening by GPO Tri fluvac and Active Comparator Group

Note: - Enrolled cases will be compared between GPO Tri fluvac and Active Comparator.

	Enr	Enrolled			
	Tri fluvac (N=xx)	Comparator (N=xx)			
Urine Pregnancy Test, n (%)					
Positive					
Negative					
P-	value =				

TREF 1.5: Urine Pregnancy Test at Prior Immunization (Day 0)

Note: - Enrolled cases will be compared between GPO Tri fluvac and Active Comparator.

- A urine pregnancy test will be done in females on Day 0 prior to vaccination.

2. Safety Assessment

Adverse Event

- TREF 2.1.: Summary of Treatment Emergent Adverse Event by GPO Tri fluvac and Active Comparator Group
- TREF 2.2: Comparison of Maximum Severity Grade of Adverse Event by GPO Tri fluvac and Active Comparator Group
- TREF 2.3: Summary of Adverse Events Classified by MedDRA term

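### SAP TREF 3.4 tests normal versus abnormal physical findings between arms at follow-up, although examination after screening is optional and triggered by history or symptoms, and the table has no row for the unexamined and no stated denominator

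*SAP*

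**What the plan says.** **Protocol.** The section on general physical examinations (8.11.3) states: "Qualified study clinicians will conduct a physical examination of all participants at S1". Table 2 marks the examination as optional at Days 0, 7, 21 and 90, and remark a explains: "Only at screening, the rest when the history suggested". The targeted-examination paragraph of 8.11.3 adds: "If no symptoms are reported by the participant, the Targeted PE does not need to be performed". Section 7.4.1 (Day 7) says: "A study clinician will perform a targeted (symptom based) physical examination and record the information on the CRF". Section 10.5 also makes examination at follow-up depend on the history. The visit lists for Day 21 (7.4.2) and Day 90 (7.4.4) mention no examination. Table 2, remark e, allows screening and immunisation on the same day.

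**SAP.** The universal examination has its own table, "TREF 1.4: Physical Examination at Screening by GPO Tri fluvac and Active Comparator Group". The follow-up table is "TREF 3.4: Physical Examination by GPO Tri Fluvac and Active Comparator Group". It sets the two arms side by side at Days 0, 7, 21 and 90, with Normal and Abnormal counts and percentages for HEENT, lungs, cardiovascular, gastrointestinal, musculoskeletal, skin and neurologic findings, and a p-value row for each system. It carries no note on who is included.

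**The concern.** The layout suits a measurement taken on everyone at every visit, such as the vital signs in TREF 3.3, which Table 2 schedules without condition at Days 7, 21 and 90. It does not suit an examination that is triggered.

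Who is examined at Days 7, 21 and 90 is settled after vaccination and can depend on reactions to the assigned product. If percentages are taken among those examined, the arms are no longer compared as randomised. An arm with more mild symptoms and normal examinations gains normal results, and its abnormal percentage falls. If N is everyone and the two rows must add up to it, people nobody examined are reported as normal. The shell does not say which applies, so the reader of a between-arm safety table could not interpret its p-values.

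**Working it through.** The plan gives no figure on this point, so there is none to reproduce. The check has three steps.

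**1. Compare with other SAP shells.**

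| Shell | Restricted set or denominator stated | Row for not done |
|---|---|---|
| TREF 2.8 (examination at influenza-like illness) | Yes: only participants with such illness | No |
| TREF 2.9 (RT-PCR) | Yes: same restriction | Yes |
| TREF 3.8, 3.9 (local reactions) | Yes: percentages of all enrolled | Not needed |
| TREF 3.4 (examination at visits) | No | No |

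**2. Count the cells.** Seven systems × 4 visits = 28. Days 7, 21 and 90 account for 7 × 3 = 21, and these are the cells that vaccine reactions can influence. The other 7 are Day 0. There the issue is a possible mixture of full examinations (screening on the same day) and triggered ones.

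**3. Show what an examined-only denominator can do.** Arm sizes of 630 and 315 come from the protocol. Every rate below is an assumption. Let a = 3% of participants in *both* arms have an abnormal finding in the tested system, all of them among a share s who are ill and examined. Let a further share r be examined for reaction symptoms and found normal. The rate among those examined is a/(s + r).

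| s | r, Tri Fluvac / comparator | Number examined | Abnormal among examined | Abnormal among all | Chance of p<0.05 |
|---|---|---|---|---|---|
| 10% | 0% / 0% | 63 / 32 | 30% v 30% | 3% v 3% | nominal 5% |
| 10% | 10% / 10% | 126 / 63 | 15% v 15% | 3% v 3% | nominal 5% |
| 10% | 20% / 10% | 189 / 63 | 10% v 15% | 3% v 3% | about 21% |
| 10% | 20% / 5% | 189 / 47 | 10% v 20% | 3% v 3% | about 48% |
| 5% | 32.5% / 19% | 236 / 76 | 8.0% v 12.5% | 3% v 3% | about 24% |

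The last row borrows the vaccine and placebo pain rates from the phase I/II results in Protocol 2.4, only to set a range. The comparator here is an active vaccine, so its gap may be smaller.

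The chance of p<0.05 is Φ[(|p₁ − p₂| − 1.96·SE₀)/SE₁], where SE₀ uses the pooled rate and SE₁ the separate rates. For the third row:
- pooled rate = (18.9 + 9.45)/252 = 0.1125
- SE₀ = √[0.1125 × 0.8875 × (1/189 + 1/63)] = 0.0460
- SE₁ = √(0.09/189 + 0.1275/63) = 0.0500
- Φ[(0.05 − 1.96 × 0.0460)/0.0500] = Φ(−0.80) ≈ 0.21

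With equal examination there is no bias between arms, although the tabulated rate still moves (30% or 15% against a true 3%). With unequal examination, a difference appears where none exists.

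**The case against.** **The denominator is unknown, so no distortion is certain.** This stands. TREF 3.4 shows only a placeholder for N, and other SAP tables use all cases or all enrolled. If N is everyone in the arm at the visit, the Abnormal percentage is already a sound measure. What remains on that reading is that the unexamined are counted as normal or drop out of both rows.

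**A reader might infer that abnormal rates will jump after vaccination, or that the direction between arms will reverse.** The documents support neither. Both need the examined-only reading, and TREF 3.4 has no screening column from which to read a trend. A reversal can be constructed: 38/126 v 16/32 (30% v 50%) gives Fisher p = 0.039, while the same counts over all randomised, 38/630 v 16/315 (6.0% v 5.1%), give p = 0.66. But those counts are invented and put every abnormality in one body system. Spread over seven systems, at about 5/126 v 2/32 or 6/126 v 3/32, p is about 0.63 or 0.39. The step 3 table likewise assumes 3% within one system.

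**A reader might infer that all 28 p-values are distorted by reactions.** If the Day 0 examination precedes vaccination, as its place among the entry checks in Table 2 suggests, the assigned vaccine cannot drive who is examined. In addition, p-value placeholders are filled only under Day 0 for HEENT and neurologic. The rest are implied by the repeated rows.

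**Examination without symptoms is not barred.** Correct: it is optional, and 7.4.1 could be read as a routine Day 7 step. But 8.11.3 waives it when no symptoms are reported.

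**Physical examination is not an endpoint.** Correct, and this limits the weight of the point. Primary safety rests on solicited events, unsolicited events and SAEs, which have their own tables.

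**Conclusion.** The mismatch holds. A two-row table with a between-arm p-value is unsuited to an examination done at clinical discretion, and the missing denominator leaves two readings, each with a fault. It affects up to 21 cells at Days 7, 21 and 90 through selection after vaccination, and leaves the 7 Day 0 cells of mixed origin.

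The size cannot be fixed from the documents. If N is those examined and examination rates differ between arms, the assumed cases above give about a 21% to 48% chance of a nominally significant result with no true difference. If examination rates are equal, or N is everyone attending, that bias between arms does not arise.

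The consequence is confined to a supportive safety table. The non-inferiority conclusion and the primary safety endpoints are unaffected. The shell should still be changed, because the correction is simple and removes an avoidable selection bias from a between-arm safety comparison.

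**What to change.** In TREF 3.4:

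- Take as denominator all vaccinated participants attending the visit, and state it in a note.
- Use three rows per system and arm: not examined; examined, normal; examined, abnormal.
- Report examined-and-abnormal over that denominator, descriptively or as a risk difference with a 95% CI.
- Remove the normal-versus-abnormal p-values among those examined.
- Add a footnote that examination after screening was triggered, so signs in participants without symptoms may have gone undetected, and that Day 0 may combine full and triggered examinations.

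The cost is a revised table shell and its programming. No new data are needed, provided the CRF separates not examined from normal; the documents do not show the CRF, so this should be confirmed. Undetected signs in participants without symptoms remain a limitation that no table layout removes.
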